2.1. Purpose of the Analyses

The overall goal is to assess the safety and efficacy of auranofin compared to a placebo for the treatment of asymptomatic amebiasis and giardiasis among males and non-pregnant females aged 18-65 years old in Bangladesh in two study populations: asymptomatic and symptomatic.

Two analyses will be conducted – one for the asymptomatic patients and another for the symptomatic patients, each according to their corresponding outcome measures. This SAP includes analysis plans for both study populations.

3. STUDY OBJECTIVES AND ENDPOINTS

3.1. Study Objectives

Auranofin is a “repurposed” drug with established pharmacology and is approved for human use by the FDA. This study assesses clinical efficacy for two new indications, amebiasis and giardiasis, with a randomized Phase IIa, placebo-controlled, single-blinded, superiority trial comparing auranofin for treatment of amebiasis and giardiasis to placebo. Parasite clearance will be analyzed in the asymptomatic population, while resolution of diarrhea will be studied in the symptomatic population. Ultimately, the goal will be to expand the trial to include symptomatic children after proving efficacy and safety in adults.

All subjects will have the same screening protocol, but the trial will evaluate subjects with amebiasis or giardiasis with separate primary and secondary endpoints. Below, objectives for the asymptomatic population are excerpted below from Version 4.0 of the Study Protocol, the first version under which participants were enrolled, and those for the symptomatic population are excerpted below from Version 7.0 of the Study Protocol.

3.1.1. Objectives for the Asymptomatic Population

Primary *E. histolytica*:

To compare the proportion of subjects with parasitological response (no detection of cysts or trophozoites of *E. histolytica* on microscopic exam or negative antigen detection) by Day 7

Secondary *E. histolytica*:

1. To compare the proportion of subjects with parasitological response (no detection of cysts or trophozoites on microscopic exam or negative antigen detection) by Day 3 and 5
2. To compare the rate of decrease in trophozoite/cyst load by qPCR in stools by Days 3, 5, and 7
3. To compare the proportion of subjects with negative stool antigen test by Days 3, 5, 7, and 14
4. To compare the proportion of subjects with sustained cure (no detection of cysts or trophozoites by microscopic exam or negative antigen detection) at 14 and 28 days
5. To compare the proportion of subjects with relapse (same strain) or re-infection (new strain) with positive stools at 14 and/or 28 days by genotyping the initial vs. subsequent strain

Primary *Giardia*:

To compare the proportion of subjects with parasitological response (no detection of cysts or trophozoites on microscopic exam or negative antigen detection) by Day 5

Secondary *Giardia*:

1. To compare the proportion of subjects with parasitological response (no detection of cysts or trophozoites on microscopic exam or negative antigen detection) by Day 3
2. To compare the rate of decrease in trophozoite/cyst load by qPCR in stools by Days 3 and 5
3. To compare the proportion of subjects with sustained cure (no detection of cysts or trophozoites by microscopic exam or negative antigen detection) at 14 and 28 days

4. To compare the proportion of subjects with relapse (same strain) or re-infection (new strain) with positive stools at 14 and/or 28 days by genotyping the initial vs. subsequent strain

3.1.2. Objectives for the Symptomatic Population

Primary *E. histolytica*:

To compare the proportion of subjects with stools positive by rapid EIA and positive antigen detection EIA for *E. histolytica* at enrollment with resolution of diarrhea (less than 3 loose stools/ 24 hours) by Day 7.

Secondary *E. histolytica*:

- To compare the proportion of subjects with positive rapid EIA and positive antigen detection EIA for *E. histolytica* and trophozoites on smear (wet mount or concentrated trichrome) at enrollment with parasitological response (no detection of trophozoites on microscopic exam) by Day 7.
- To compare the proportion of subjects with positive rapid EIA and positive antigen detection EIA for *E. histolytica* and trophozoites on smear at enrollment with parasitological response (no detection of trophozoites on microscopic exam) by Day 3 and 5.
- To compare the rate of decrease in trophozoite/cyst load by qPCR in stools by Days 3, 5, and 7.
- To compare the proportion of subjects with negative stool antigen test by Days 3, 5, 7, and 14.
- To compare the proportion of subjects with sustained cure (no detection of trophozoites by microscopic exam) at 14 and 28 days.
- To compare the proportion of subjects with relapse (same strain) or re-infection (new strain) with positive stools at 14 and/or 28 days by genotyping the initial vs. subsequent strain.
- To compare the time to resolution of diarrhea (less than 3 loose stools/24 hours)

Primary *Giardia*:

To compare the proportion of subjects with stool positive rapid EIA and positive antigen detection EIA for *Giardia* at enrollment with resolution of diarrhea (less than 3 loose stools/24 hours) by Day 5.

Secondary *Giardia*:

- To compare the proportion of subjects with parasitological response (no detection of trophozoites on microscopic exam) by Day 3 and 5.
- To compare the rate of decrease in trophozoite/cyst load by qPCR in stools by Days 3 and 5.
- To compare the proportion of subjects with negative stool antigens by days 3 and 5.
- To compare the proportion of subjects with sustained cure (no detection of trophozoites by microscopic exam) at 14 and 28 days.
- To compare the proportion of subjects with relapse (same strain) or re-infection (new strain) with positive stools at 14 and/or 28 days by genotyping the initial vs. subsequent strain.
- To compare the time to resolution of diarrhea (less than 3 loose stools/24 hours)

3.2. Endpoints

The asymptomatic endpoints are excerpted below from the Study Protocol, Version 4.0 (the first version under which participants were enrolled), and the symptomatic endpoints are excerpted from the Study Protocol, Version 7.0.

3.2.1. Asymptomatic Population Endpoints

Primary Outcome Measures

1. Proportion of subjects with parasitological response of *E. histolytica* (no detection of cysts or trophozoites of *E. histolytica* on microscopic exam or negative antigen detection) by Day 7.
2. Proportion of subjects with parasitological response of *Giardia* (no detection of cysts or trophozoites on microscopic exam or negative antigen detection) by Day 5

Secondary Outcome Measures

1. *E. histolytica*:
 - a. Proportion of subjects with parasitological response (no detection of cysts or trophozoites on microscopic exam or negative antigen detection) by Day 3 and 5
 - b. Rate of decrease of trophozoite/cyst load by qPCR in stools by Days 3, 5, and 7
 - c. Proportion of subjects with negative stool antigen test by Days 3, 5, 7, and 14
 - d. Proportion of subjects with sustained cure (no detection of cysts or trophozoites by microscopic exam or negative antigen detection) at 14 and 28 days
 - e. Proportion of subjects with relapse (same strain) or re-infection (new strain) with positive stools at 14 and 28 days by genotyping the initial vs. subsequent strain
2. *Giardia*:
 - a. Proportion of subjects with parasitological response (no detection of cysts or trophozoites on microscopic exam or negative antigen detection) by Day 3
 - b. Rate of decrease of trophozoite/cyst load by qPCR in stools by Days 3 and 5
 - c. Proportion of subjects with sustained cure (no detection of cysts or trophozoites by microscopic exam or negative antigen detection) at 14 and 28 days
 - d. Proportion of subjects with relapse (same strain) or re-infection (new strain) with positive stools at 14 and 28 days by genotyping the initial vs. subsequent strain

3.2.2. Symptomatic Population Endpoints

Primary Outcome Measures

1. Proportion of subjects with positive rapid EIA and positive antigen detection EIA for *E. histolytica* and resolution of diarrhea (less than 3 loose stools/ 24 hours) by Day 7.
2. Proportion of subjects with positive rapid EIA and positive antigen detection EIA for *Giardia* and resolution of diarrhea (less than 3 loose stools/24 hours) by Day 5.

Secondary Outcome Measures

1. *E. histolytica*:

- a. Proportion of subjects with positive rapid EIA and positive antigen detection EIA for *E. histolytica* and trophozoites on smear at enrollment with parasitological response (no detection of trophozoites on microscopic exam) by Day 7.
- b. Proportion of subjects with positive rapid EIA and positive antigen detection EIA for *E. histolytica* and trophozoites on smear at enrollment with parasitological response (no detection of trophozoites on microscopic exam) by Day 3 and 5.
- c. Rate of decrease of trophozoite/cyst load by qPCR in stools by Days 3, 5, and 7
- d. Proportion of subjects with negative stool antigen test by Days 3, 5, 7, and 14
- e. Proportion of subjects with sustained cure (no detection of trophozoites by microscopic exam) at 14 and 28 days
- f. Proportion of subjects with relapse (same strain) or re-infection (new strain) with positive stools at 14 and 28 days by genotyping the initial vs. subsequent strain
- g. Time to resolution of diarrhea (less than 3 loose stools/24 hours)

2. *Giardia*:

- a. Proportion of subjects with positive rapid EIA and positive antigen detection EIA for *Giardia* and trophozoites on smear at enrollment with parasitological response (no detection of trophozoites on microscopic exam) by Day 3 and 5
- b. Rate of decrease of trophozoite/cyst load by qPCR in stools by Days 3 and 5
- c. Proportion of subjects with negative stool antigens by days 3 and 5.
- d. Proportion of subjects with sustained cure (no detection of trophozoites by microscopic exam) at 14 and 28 days
- e. Proportion of subjects with relapse (same strain) or re-infection (new strain) with positive stools at 14 and 28 days by genotyping the initial vs. subsequent strain
- f. Time to resolution of diarrhea (less than 3 loose stools/24 hours)

3.3. Study Definitions and Derived Variables

For the purposes of enrollment into the asymptomatic population, potential subjects are *diagnosed with amebiasis or giardiasis* if they have a positive TechLab antigen test, positive wet mount or trichrome, and positive stool PCR for *E. histolytica* or *Giardia*. In order to enroll, the subject must receive the diagnosis of amebiasis or giardiasis within 72 hours of enrollment. If a subject is infected with both *E. histolytica* and *Giardia*, they will be enrolled in the *E. histolytica* study arm. Once the *E. histolytica* study arm is fully enrolled, any subsequent dual infected subjects will be enrolled in the *Giardia* arm.

For enrollment into the symptomatic population, potential subjects are *diagnosed with amebiasis or giardiasis* if they have a positive rapid EIA and positive antigen detection EIA of *E. histolytica* or *Giardia*. These subjects must also have diarrhea (3 or more loose stools within 24 hours of enrollment). In order to enroll, the subject must receive the diagnosis of amebiasis or giardiasis within 4 days prior to enrollment. If a subject is infected with both *E. histolytica* and *Giardia*, they will be enrolled in the *E. histolytica* study arm. Once the *E. histolytica* study arm is fully enrolled, any subsequent dual infected subjects will be enrolled in the *Giardia* arm. If a subject is infected with both *Giardia* and *Cryptosporidium*, they will not be enrolled.

Parasitological response is defined as no detection of cysts or trophozoites on microscopic exam or negative antigen detection, for the asymptomatic population. Both tests will be performed on each subject. For the symptomatic population, however, **parasitological response** is defined as no detection of trophozoites on microscopic exam. The microscopic exam may include both wet mount and trichrome staining. If both were performed, then both must be negative for the microscopic exam to be negative.

Sustained cure on Day 14 is defined, for the asymptomatic amebiasis group, to be no detection of cysts or trophozoites on microscopic exam or negative antigen detection on Day 7 and again on Day 14. ***Sustained cure on Day 14*** is defined, for the symptomatic amebiasis group, to be no detection of trophozoites on microscopic exam on Day 7 and again on Day 14. ***Sustained cure on Day 14*** is defined analogously for the giardiasis groups but is based on measurements taken on Day 5 and 14.

Sustained cure on Day 28 is defined for the asymptomatic amebiasis group to be no detection of cysts or trophozoites on microscopic exam or negative antigen detection on Days 7, 14, and 28 (if specimens are obtained at each time point). ***Sustained cure on Day 28*** is defined for the symptomatic amebiasis group to be no detection of trophozoites on microscopic exam on Days 7, 14, and 28 (if specimens are obtained at each time point). It is defined analogously for the giardiasis groups but is based on measurements taken on Day 5, 14, and 28.

Relapse at Day X is defined as having a positive stool PCR at day X that is identified via genotyping to be identical to the strain of the original infection.

Reinfection at Day X is defined as having a positive stool PCR at day X that is identified via genotyping to be non-identical to the strain of the original infection.

In the two above definitions, the ***original infection*** is defined to be the strain of parasite measured in the stool sample collected on Visit 01.

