Secondary objectives for the asymptomatic population are summarized in [Table 2](#), while those for the symptomatic population are summarized in [Table 3](#). The changes in secondary outcomes for the symptomatic population are shown in blue in [Table 3](#).

Table 2: Secondary Outcomes for the Asymptomatic Study Population

Outcome	Time points, Asymptomatic Amebiasis Group	Time points, Asymptomatic Giardiasis Group
Parasitological response (no detection of cysts or trophozoites on microscopic exam or negative antigen detection)	Days 3 and 5	Day 3
Rate of decrease in trophozoite/cyst load by qPCR in stools	Days 3, 5, and 7	Days 3 and 5
Negative stool antigen test	Days 3, 5, 7, and 14	N/A
Sustained cure (no detection of cysts or trophozoites by microscopic exam or negative antigen detection)	Days 14 and 28	Days 14 and 28
Relapse (same strain) or re-infection (new strain) with positive stools by genotyping the initial vs. subsequent strain.	Day 14 and/or 28	Day 14 and/or 28

Table 3: Secondary Outcomes for the Symptomatic Study Population

Changes to outcomes from the asymptomatic population are shown in blue:

Outcome	Time points, Symptomatic Amebiasis group	Time points, Symptomatic Giardiasis group
Parasitological response (no detection of trophozoites on microscopic exam ^a)	Days 3, 5, and 7 ^b	Day 3 and 5 ^b
Rate of decrease in trophozoite/cyst load by qPCR in stools	Days 3, 5, and 7	Days 3 and 5
Negative stool antigen test	Days 3, 5, 7, and 14	Days 3 and 5
Sustained cure (no detection of trophozoites by microscopic exam) ^c	Days 14 and 28	Days 14 and 28
Relapse (same strain) or re-infection (new strain) with positive stools by genotyping the initial vs. subsequent strain.	Day 14 and/or 28	Day 14 and/or 28
Time to resolution of diarrhea ^d	Assessment over the study period	Assessment over the study period

^a The definition of parasitological response was revised to allow for cysts and remove the antigen test.^b Moved from primary to secondary outcome.^c Modified so definition of “cure” matches the updated definition of parasitological response for this population.^d New outcome for this study population.

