4.3.2.1. Inclusion Criteria, Symptomatic Population

1. Provide written informed consent prior to initiation of any study procedures.
2. Able to understand and comply with planned study procedures and be available for all study visits.
3. Male or non-pregnant, non-lactating females 18-65 years of age, inclusive. Females of reproductive potential currently using effective contraceptive methods are eligible.
4. Amebiasis or giardiasis identified by rapid EIA and positive antigen detection EIA of stool¹

¹If a subject is infected with both *E. histolytica* and *Giardia*, they will be enrolled in the *E. histolytica* study arm. Once the *Entamoeba* study arm is fully enrolled, any subsequent dual infected subjects will be enrolled in the *Giardia* arm. If a subject is infected with both *Giardia* and *Cryptosporidium*, they will not be enrolled.

5. Has diarrhea (defined as three or more loose stools) in the past 24 hrs, but is assessed to be clinically stable and in otherwise good health².

²As determined by medical history and targeted physical examination, if indicated based on medical history, to evaluate acute or currently ongoing chronic medical diagnoses or conditions that would affect the assessment of eligibility and safety of subjects. Existing medical diagnoses or conditions (except those in the Subject Exclusion Criteria) must be deemed as stable chronic medical conditions. A stable chronic medical condition is defined as no change in prescription medication, dose, or frequency of medication in the last 3 months (90 days) and health outcomes of the specific disease are considered to be within acceptable limits in the last 6 months (180 days). Any change due to change of health care provider, insurance company, or that is done for financial reasons, as long as in the same class of medication, will not be considered a violation of this inclusion criterion. Any change in prescription medication due to improvement of a disease outcome, as determined by the site principal investigator or appropriate sub-investigator, will not be considered a violation of this inclusion criterion. Subjects may be on chronic or as needed (prn) medications if, in the opinion of the site principal investigator or appropriate sub-investigator, they pose no additional risk to subject safety. Topical, nasal, and inhaled medications, vitamins, and contraceptives are permitted.

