4.5. Efficacy and Safety Variables

4.5.1. Efficacy Variables

[Table 4](#) and [Table 5](#) summarize the efficacy variables and time points for the asymptomatic and symptomatic populations, respectively.

Table 4: Efficacy Variables for the Asymptomatic Study Population

Outcome Type	Outcome	Time points, Asymptomatic amebiasis group	Time points, Asymptomatic giardiasis group
Primary	Parasitological response (no detection of cysts or trophozoites on microscopic exam or negative antigen detection)	Day 7	Day 5
Secondary	Parasitological response (no detection of cysts or trophozoites on microscopic exam or negative antigen detection)	Days 3 and 5	Day 3
	Rate of decrease in trophozoite/cyst load by qPCR in stools	Days 3, 5, and 7	Days 3 and 5
	Negative stool antigen test	Days 3, 5, 7, and 14	N/A
	Sustained cure (no detection of cysts or trophozoites by microscopic exam or negative antigen detection)	Days 14 and 28	Days 14 and 28
	Relapse (same strain) or re-infection (new strain) with positive stools by genotyping the initial vs. subsequent strain.	Day 14 and/or 28	Day 14 and/or 28

Table 5: Efficacy Variables and Time Points for the Symptomatic Study Population

Changes from outcomes for the asymptomatic population are shown in blue:

Outcome Type	Outcome	Time points, Symptomatic amebiasis group	Time points, Symptomatic giardiasis group
Primary	Resolution of diarrhea ^a	Day 7	Day 5
Secondary	Parasitological response (no detection of trophozoites on microscopic exam ^b)	Days 3, 5, and 7 ^c	Day 3 and 5 ^c
	Rate of decrease in trophozoite/cyst load by qPCR in stools	Days 3, 5, and 7	Days 3 and 5
	Negative stool antigen test	Days 3, 5, 7, and 14	Days 3 and 5
	Sustained cure (no detection of trophozoites by microscopic exam) ^d	Days 14 and 28	Days 14 and 28
	Relapse (same strain) or re-infection (new strain) with positive stools by genotyping the initial vs. subsequent strain.	Day 14 and/or 28	Day 14 and/or 28
	Time to resolution of diarrhea	Assessment over the study period	Assessment over the study period

^a New outcome for the symptomatic population^b The definition of parasitological response was revised to allow for cysts and remove the antigen test.^c Moved from primary to secondary outcome.^d The definition of “cure” was updated to match the updated definition of “parasitological response”.

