6.3.1.1. Exclusions Due to Violation of Eligibility Criteria

Furthermore, subjects who meet the primary outcome at baseline (and therefore should not have been enrolled) will be excluded from the mITT population. In the asymptomatic population, the outcome is a negative microscopy or antigen test at Day 5 or 7, so subjects were required to have both positive microscopy result and positive test result for their respective disease in order to enroll. Those who did not will be excluded.

In the symptomatic population, subjects were to have amebiasis or giardiasis identified by rapid EIA and positive antigen detection at enrollment in order to be eligible. The primary outcome is resolution of diarrhea by Day 5 or 7. Those who either failed the eligibility criterion (i.e., had a negative EIA or negative antigen test), or did not have diarrhea at enrollment, will be excluded from the mITT population.

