Table 28: Comparison of Proportion of Subjects with Negative Stool Antigen Test between Auranofin Group and Placebo Group, Asymptomatic Amebiasis Group

		Proportion with negative stool antigen tests (95% CI) on the specified day					
	Number of Subjects	During Screening	Day 1	Day 3	Day 5	Day 7	Day 14
Auranofin, 6 mg							
Placebo							
Difference in clearance rates (95% CI)							

Note: These analyses will be performed both on the m-ITT population and the per-protocol population.
 Footnote 1: The method for CI calculation will be denoted here.

Table will be repeated for the symptomatic population

Table 29: Comparison of Proportion of Subjects with Sustained Cure between Auranofin Group and Placebo Group, Asymptomatic Amebiasis Group

		Proportion with sustained cure on the specified day and 95% CI		
	Number of Subjects	Day 7	Day 14	Day 28
Auranofin, 6 mg				
Placebo				
Difference in clearance rates (95% CI)				

The following definitions are for the asymptomatic amebiasis group:
Sustained cure on Day 14 is defined as no detection of cysts or trophozoites on microscopic exam or negative antigen detection on Days 7 and 14.
Sustained cure on Day 28 is defined to be no detection of cysts or trophozoites on microscopic exam or negative antigen detection on Days 7, 14, and 28.
Note: These analyses will be performed both on the m-ITT population and the per-protocol population.
Footnote 1: The method for CI calculation will be denoted here.

Table will be repeated for the symptomatic population.

Footnotes for the repeat table:

Sustained cure on Day 14 is defined to be no detection of trophozoites on microscopic exam on Days 7 and 14.

Sustained cure on Day 28 is defined to be no detection of trophozoites on microscopic exam on Days 7, 14, and 28.

Table 30: Comparison of Proportion of Subjects with Sustained Cure between Auranofin Group and Placebo Group, Asymptomatic Giardiasis Group

		Proportion with sustained cure on the specified day and 95% CI		
	Number of Subjects	Day 5	Day 14	Day 28
Auranofin, 6 mg				
Placebo				
Difference in clearance rates (95% CI) for the difference				

The following definitions are for the asymptomatic giardiasis group:
Sustained cure on Day 14 is defined to be no detection of cysts or trophozoites on microscopic exam or negative antigen detection on Days 5 and 14.
Sustained cure on Day 28 is defined to be no detection of cysts or trophozoites on microscopic exam or negative antigen detection on Days 5, 14, and 28.

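### Relapse as defined counts infection that never cleared, and symptomatic sustained cure does not separate out subjects with no trophozoites detected at baseline

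*SAP*

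**What the plan says.** **Relapse and reinfection (both populations).** SAP 3.3 defines relapse at Day X as a PCR-positive stool on that day whose genotype is identical to the Visit 01 strain, and reinfection as one whose genotype is not identical. Neither asks for a negative stool in between. SAP 8.2.1 applies the same analysis to the symptomatic population, and Tables 31-34 are repeated for it. Protocol 8.2.1 sends for genotyping the stools that are still positive at Days 14 and 28.

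**Sustained cure (symptomatic).** In SAP 3.3, Day 14 cure "is defined, for the symptomatic amebiasis group, to be no detection of trophozoites on microscopic exam on Day 7 and again on Day 14". Giardiasis uses Days 5 and 14, and Day 28 cure adds the Day 28 stool. The endpoint list in SAP 3.2.2 has only "Proportion of subjects with sustained cure (no detection of trophozoites by microscopic exam) at 14 and 28 days". The symptomatic footnote to Table 29 agrees: "Sustained cure on Day 14 is defined to be no detection of trophozoites on microscopic exam on Days 7 and 14".

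**Who is in the denominator.** Symptomatic entry is "Amebiasis or giardiasis identified by rapid EIA and positive antigen detection EIA of stool", plus diarrhea. SAP 6.3.1.1 removes only subjects who "had a negative EIA or negative antigen test), or did not have diarrhea at enrollment, will be excluded from the mITT population". Microscopy plays no part in either.

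**The parallel endpoint.** In the same SAP 3.2.2 list, parasitological response is limited to subjects with positive EIA results "and trophozoites on smear at enrollment with parasitological response (no detection of trophozoites on microscopic exam) by Day 3 and 5". Table 3 note c says the cure definition "matches the updated definition of parasitological response for this population", and Table 5 note d says it "was updated to match the updated definition of" response.

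**The concern.** Relapse normally means return after clearance. As written, the relapse proportion adds together persistent infection and true relapse. If the arms differ in clearance, Tables 31-34 will show an arm difference in relapse even when relapse risk after clearance is the same, and a reader will take it as a second, independent benefit.

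For cure, the symptomatic proportion pools subjects who lost detectable trophozoites with subjects in whom none were detected at the start. Asymptomatic subjects had to be microscopy-positive to enroll, so the gap arose when the population changed. The notes linking cure to response do not close it, because SAP 3.3 defines response without a baseline condition too; the smear limit stands only in the outcome and endpoint descriptions.

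**Working it through.** **Inputs.** The documents give no rates for sustained cure or relapse and no share of symptomatic subjects with trophozoites on the baseline smear. I borrow the planning rates for the primary outcome (SAP 5): 80% versus 20% in amebiasis, using the upper end of the 15-20% placebo range, and 70% versus 30% in giardiasis. I use 30 completers per arm, from the 60 stated for amebiasis and assumed the same for giardiasis. Everything else below is assumed and varied.

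**The plan's own figures.** Exact two-sided Fisher power (p <= 0.05) for 80% versus 20% at 30 per arm is 99.8%, consistent with the stated more than 95%. For 70% versus 30% it is 83.8% at 30 per arm and 87.6% at 34, against a stated 85%. The planning figures are not in dispute.

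**Relapse.** Let c be the proportion cleared, r the relapse risk after clearance (10% in both arms) and s the share of uncleared subjects who are same-strain positive at Day X.

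Reported relapse = (1 - c) x s + c x r

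Amebiasis, s = 100%: auranofin 0.20 x 1 + 0.80 x 0.10 = 28%; placebo 0.80 x 1 + 0.20 x 0.10 = 82%.

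| s | Amebiasis, auranofin vs placebo | Chance Fisher p <= 0.05 | Giardiasis, auranofin vs placebo | Chance Fisher p <= 0.05 |
|---|---|---|---|---|
| 100% | 28% vs 82% | 98.9% | 37% vs 73% | 74.3% |
| 75% | 23% vs 62% | 82.2% | 29.5% vs 55.5% | 43.3% |
| 50% | 18% vs 42% | 43.0% | 22% vs 38% | 19.0% |
| 25% | 13% vs 22% | 7.9% | 14.5% vs 20.5% | 4.4% |

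After a split on the full arm denominator (amebiasis, s = 100%), relapse is c x r = 8% versus 2% and persistent infection is (1 - c) x s = 20% versus 80%. Relapse alone then runs against the arm that clears more, simply because more of its subjects are at risk.

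Sparse sampling limits the split. If a share m = 25% of cleared subjects clear only after the last stool before Day 14, relapse reads c x (1 - m) x r = 6% versus 1.5%. The other category reads (1 - c) + c x m x r = 22% versus 80.5%.

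**Sustained cure.** Let f be the share with baseline trophozoites, p the cure rate among them, and qa and qp the percentages of smear-negative entrants (auranofin, placebo) who read negative at every required visit.

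Observed cure = f x p + (1 - f) x q, by arm

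At f = 50%, the restricted analysis has 15 per arm:

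| Disease, qa/qp | All subjects | Power, all (30 per arm) | Power, restricted (15 per arm) | Placebo cures with no trophozoites detected at baseline |
|---|---|---|---|---|
| Amebiasis 100/100 | 90% vs 60% | 70.5% | 87.2% | 83.3% |
| Amebiasis 80/80 | 80% vs 50% | 59.6% | 87.2% | 80.0% |
| Amebiasis 90/60 | 85% vs 40% | 94.0% | 87.2% | 75.0% |
| Amebiasis 80/20 (same as smear-positive) | 80% vs 20% | 99.8% | 87.2% | 50.0% |
| Giardiasis 100/100 | 85% vs 65% | 33.0% | 43.4% | 76.9% |
| Giardiasis 90/60 | 80% vs 45% | 73.8% | 43.4% | 66.7% |

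The last column is (1 - f) x qp / [f x p + (1 - f) x qp], with placebo p. Restriction gains power where smear-negative entrants read negative equally in both arms, and loses it where treatment affects them as well.

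**The case against.** *On relapse*, the defence is that this is a matter of labelling. Genotyping stools that are still positive shows that persistent infection is knowingly included, clearance and cure are tabulated separately, and Listings 15-18 show results by day. Equal clearance would create no arm difference. The largest contrast needs s = 100%, whereas Protocol Appendix B omits stool evaluation for subjects given metronidazole before completing dosing, plausibly many of the uncleared. Those points limit the size. They do not change what Tables 31-34 would report under that heading.

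*On cure*, the defence is stronger. Every eligible symptomatic subject has two positive EIA results, so infection is documented; a negative smear means trophozoites were not detected. A reader might infer that these subjects had nothing to clear, but the documents do not support that. A reader might also infer that the smear-positive subset should replace the mITT population for cure. SAP 6.3 applies mITT to all primary and secondary endpoints, that comparison is randomized, and restriction can cost substantial power. That objection stands.

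*On the Giardia response objective* (Protocol Summary, Protocol 3.1, SAP 3.1.2), the missing smear limit might be read as a contradiction. Protocol 3.2.2, 11.1 and 11.4 and SAP 3.2.2 all state it, so this is an omission.

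**Conclusion.** The relapse definition is wrong for its label in both populations: followed as written, it reports never-cleared infection as relapse. The direction is certain whenever uncleared subjects are more likely than cleared ones to be same-strain positive and the arms differ in clearance. The size is not: 28% versus 82% down to 13% versus 22% in amebiasis, under assumed rates borrowed from diarrhea resolution. In the asymptomatic population, with 34 subjects over both diseases and all arms, the point concerns description more than testing.

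The sustained cure definition is incomplete, not invalid. It needs baseline smear status beside it to be interpretable. Whether the all-subject or the restricted analysis has more power depends on the behavior of smear-negative entrants, which the documents do not give.

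It would be too strong to infer that the primary outcome or the type I error of the cure comparison is affected. The primary outcome is resolution of diarrhea in the symptomatic population and parasitological response in the asymptomatic one, and the all-mITT cure comparison keeps the randomization. These are secondary endpoints worth correcting before unblinding.

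**What to change.** 1. **Relapse (SAP 3.3, Tables 31-34, both populations).** Split same-strain positives at Day X into relapse (at least one PCR-negative stool after Day 1 and before Day X) and persistent or clearance not documented (none). Keep reinfection defined by non-identical genotype. Show all categories plus not tested on the full arm denominator, and do not interpret relapse alone as a treatment comparison.
2. **Sustained cure (SAP 3.3, symptomatic repeats of Tables 29-30).** Keep the all-mITT proportion as the randomized comparison. Add a pre-specified analysis in subjects with trophozoites on wet mount or trichrome in a stool collected before the first dose; Visit 00A already has both tests. Report the numbers with and without baseline trophozoites by arm.
3. **Clean-up.**
   - Carry the smear limit on response into the Giardia objective (Protocol and SAP together, since the SAP text is an excerpt), SAP 3.3 and the notes to Tables 24-25.
   - Reconcile the Visit 01 stool window of +1 day (Protocol 7.2) with the Appendix B Day 1 row, which describes DNA from a stool taken before the first dose.
   - Reconcile the giardiasis Day 7 stool: Protocol 7.3.6 limits it to amebiasis, while Protocol 8.2.1, SAP 4.5.1 and Table 10 include Day 7.
   - Align the genotyping trigger with the PCR-positive definition: Protocol 8.2.1 refers to cysts or trophozoites, and the Appendix B Day 28 row is conditioned on Day 14.
   - Correct the reinfection header in Listings 15-18, which repeats the relapse wording.

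**Cost.** Edits to SAP definitions, table notes and listing headers, and a short protocol clarification. The smears and qualitative PCR are already scheduled; a few extra genotyping assays may be needed. Few stools fall before Day 14, so late clearance cannot be told from persistence, which is why the second category needs its full name. The added cure analysis has a smaller denominator.
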